4. Acclimation time varies widely in the literature (from 3-10 hours [2, 3] to months [4]) and is acknowledged to have important implications for this study's results. In this study, subjects will go through an initial tuning and training process similar to what is done in clinic scenarios including tuning knee parameters and training over the various terrains in the lab including stairs, ramps and a treadmill. Subjects will then proceed to wear the prosthesis for 1 week at home and in the community in order to acclimate to the device and then return to the lab for testing. A sensor to collect data about the number of steps participants take will be attached to the prosthesis and/or your shoes. This sensor does not have a GPS and will not record where subjects go. Subjects will use their same socket, prosthetic foot and shoe during each knee evaluation to ensure that differences observed during the study are attributable to the knee.
5. Subjects will ambulate five times over the 18' instrumented gait mat to determine their self-selected walking speed (SSWS) and GVI. Subjects will complete a 2-minute walk test and then be administered the Borg RPE.[5] A heart rate monitor will be worn during the 2 minute walk test in order to calculate physiological cost index (PCI) [6]
6. Subjects will proceed to walk up and down an overground 5-degree ramp for ten trials and then walk up/down a 6-step stair case for ten trials while we measure lower body 3D biomechanics and completion speed.

7. Subjects will walk across a beam while wearing the prosthesis. The beam is very low in height and sits only ~2" inches off the ground.
8. Subjects will walk on a treadmill while wearing the prosthesis while we measure lower body 3D biomechanics.
9. Subjects will then fill out the OPUS HRQOL, LEFS, PEQ, Veteran SF-36, and fall history survey to assess their perception of performance and other health related quality of life factors associated with use of each device. Pilot work with these surveys indicates this will take approximately 30-45 minutes.
10. Subjects will repeat Steps 4-8 with periods of rest provided as necessary until they have completed the full protocol for each of the three MPKs and research grade powered knee.

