During all testing participants are instructed to vocalize any concerns or discomfort to researchers. Tests that occur in the lab will occur with the use of a safety harness and or gait belt. During tests, verbal feedback from the participants will be used to improve the comfort of the devices. Participants are instructed to notify researchers if they feel unsafe, and may quit the study at any time without penalty. Additionally, participants may be asked to wear EMG sensors, markers for measuring biomechanics and other mechanical sensors (such as IMUs) All participants will be guided through the following general procedure during their visits, requiring action on their part:

- Participants will be briefed about the details of and their rights during the study.
- The prosthesis and attachment interface will be fit to the participant, along with any additional data collection equipment.
- Participants will be guided through the specific activities of the study, detailed already.
- Participants will receive assistance removing any sensors used during the study.

Other equipment may be utilized to measure biomechanics of the user during ambulation. Specifically, we will be using a VICON motion capture analysis system and an instrumented treadmill. This will also us to measure biomechanical similarities and differences while using the powered prosthesis compared to the sound side limb. Also, some protocols will require the use of an EMG (electromyography) system to measure muscle activity across different ambulation tasks. Three systems may be used which includes the Delsys Trigno Wireless EMG system, Biometrics Ltd. EMG system, and COAPT EMG system. All of these systems will use electromyography sensors that will be placed on the surface of the user's skin.

In order to also measure functional clinical measures, a Protokinetics gait mat will be utilized to measure common measures such as step length, step time, and symmetry. This system is just a mat that users will need to walk on top similar to walking overground. Users will be in a harness and have the options for handrails or gait belt if needed.

Throughout the tests there will be a camera recording the session. The purpose of the camera is to record performance for future analysis. The participant will always have the right to stop the test and/or take a break. The participant may also choose to discontinue participation at any time.

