#### **4. Research Risks**

The prosthetic knees have hydraulics and sensors. This type of device is classified as a prosthetic component and is a FDA Class I device. This means that it is a low-risk type of medical equipment. Although these procedures are very safe and commonly used in our lab, participation in this study may involve the following risks: The primary risk of injury in this protocol would be due to falls, regardless of the prosthesis being used. To minimize this risk, participants will be asked to wear a safety harness and initially walk with handrails until they become comfortable using the prosthetic device(s) and demonstrate that they can use it without falling. Should participants fall during this familiarization session, the harness will support them. When walking overground, participants will still have the option of wearing the safety harness, access to hand rails or other walking aids, and may be supported by staff members using a gait belt as you complete the activities. When participants wear the prosthesis at home, they will not have access to a harness or gait belt. This is similar to what happens in clinical scenarios when a prosthetist fits a patient with a prosthetic component; while in the clinic, familiarization occurs and then the patient is sent home to use the device independently.

A second risk is muscle soreness and fatigue. Muscle soreness is a common

problem when walking with a new prosthesis. To prevent this, experimental sessions will be kept as short as possible, adequate rest periods will be provided between trials, and participants will be questioned often about any discomfort.

A third risk is skin irritation. Skin can become irritated while using any prosthesis and it may also become irritated by adhesive reflective markers. Additionally, the residual limb will be checked prior to and after the study to inspect for skin irritation or if participants experience discomfort in their residual limb during the study, we will give time for the socket to be removed to allow for appropriate inspection. To avoid the risk of skin irritation, participants will use your normal, take-home socket.

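### Falls are the named primary risk, but the only fall question comes after the return-visit walking tests and has no stated recall period

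*Combined protocol and SAP*

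**What the plan says.** On the hazard, section 4 (Research Risks) states: "The primary risk of injury in this protocol would be due to falls, regardless of the prosthesis being used". On home wear it adds: "When participants wear the prosthesis at home, they will not have access to a harness or gait belt".

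Section 3 (Study Procedures) sets the sequence for each knee:

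- Step 4, home period: "Subjects will then proceed to wear the prosthesis for 1 week at home and in the community in order to acclimate to the device". The only monitoring described for that week is a step counter: "A sensor to collect data about the number of steps participants take will be attached to the prosthesis and/or your shoes".
- Steps 5–8, return visit: gait mat, 2-minute walk, ten ramp trials, ten stair trials, beam and treadmill.
- Step 9, after these: "Subjects will then fill out the OPUS HRQOL, LEFS, PEQ, Veteran SF-36, and fall history survey to assess their perception of performance". The sentence goes on to mention "other health related quality of life factors associated with use of each device".
- Step 10: "Subjects will repeat Steps 4-8 with periods of rest provided as necessary". Step 9 lies outside that range.

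Step 3, before the first test knee, lists the preference survey and the AMPnoPro but no fall survey. No recall period for falls appears anywhere. The general safety instruction in section 3 reads: "During all testing participants are instructed to vocalize any concerns or discomfort to researchers". Section 11 says that the three commercial knees are the ones taken home, whereas Steps 4 and 10 read as if home wear applied to all four.

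**The concern.** The home week is the least protected exposure to the hazard that the protocol ranks first, yet no step asks about a home fall until the lab tests are over. Whoever runs the ramp, stair, beam and treadmill tests may therefore start them without knowing that the participant fell on that knee during the week.

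The second issue is attribution. Each participant wears several knees in sequence, and a fall history without a stated period can reach back past the current knee. If fall reports are later used to describe the knees or to inform the Aim 3 algorithm, a fall needs to be tied to the knee worn when it happened.

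**Working it through.** The documents give no fall rate, fall endpoint or power for falls, so there is no planned figure to reproduce. The check is mainly one of reading; the arithmetic in points 3 to 5 only sets the scale.

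**1. Order within a visit.** Steps 5–8 come first and Step 9 follows. No earlier step in the loop asks about falls, and Step 4 records only step counts. No diary, call or fall report is described for the home week.

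**2. Other routes by which a fall could surface.**

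- Voicing concerns or discomfort (section 3): volunteered, and worded for testing.
- Telling researchers about feeling unsafe (section 3): volunteered, not limited to testing, but not a question about past falls.
- Questions about discomfort, and skin checks (section 4): asked or done by staff, but aimed at soreness and skin.

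Any of these could bring out a fall. None asks about one.

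**3. Length of the delay.** Section 3 puts testing at 2–6 hours per subsequent visit, and Step 9 estimates 30–45 minutes for the questionnaires. If the questionnaires are counted within the visit (an assumption), the time from arrival to Step 9 is roughly 2 h − 0.75 h = 1.25 h at the shortest and 6 h − 0.5 h = 5.5 h at the longest. If they are not counted, it is the full 2–6 hours.

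**4. Recall window (illustration).** Let the survey look back W weeks, and let the current knee's home period be 1 week (Step 4). With a constant fall rate, the share of the window outside that home period is 1 − 1/W. Every value of W above 1 is an assumption.

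| W (weeks) | Share outside the home week |
|---|---|
| 1 | 0% |
| 2 | 50% |
| 4 | 75% |
| 12 | 92% |
| 26 | 96% |
| 52 | 98% |

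Tying the window to the 1-week home period reduces the share to 0%.

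**5. Is a home fall likely to arise at all?** With 17 participants and the three home-worn knees of section 11, there are 17 × 3 = 51 home weeks; if all four knees go home, 17 × 4 = 68. The documents give no weekly fall probability p. Assuming independent weeks with the same p, the expected number of home weeks with a fall is 51p, and the chance of at least one is 1 − (1 − p)^51:

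- p = 0.01: 0.51 expected; chance 40%
- p = 0.05: 2.55 expected; chance 93%
- p = 0.10: 5.1 expected; chance 99.5%

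Across this assumed range, the situation is plausible at least once, but the counts would be small.

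**The case against.** The opposing case is substantial, and part of it stands.

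- **The form may have its own window.** It is not in the documents, and Step 9 says the surveys concern use of each device. This stands: a reader might infer that falls will be credited to the wrong knee, but the text shows only that it could happen. A statement of purpose is still not a recall period, and a window on the form would not change the order of the visit.
- **Other safety routes exist, and lab tests use a harness or gait belt.** This also stands in part. A fall need not stay hidden, and the lab is not the unprotected setting. The consent form, not available here, may contain instructions for the home week. The procedures as written still leave it to the participant to raise the fall.
- **The gain is only hours.** True. Asking on arrival does not provide surveillance during the home week; it puts the answer before the tests instead of after them.
- **Knee order is randomized.** On average, spillover from earlier periods would blur differences between knees rather than favour one. This is a further reason not to call it a demonstrated bias.

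Three stronger readings are tempting and not supported. First, one might infer that a misassigned fall or two would alter the ranking of the knees; the statistical plan defines no fall endpoint, fall analysis or ranking. Second, zero falls in 17 home weeks would be compatible with a weekly risk of up to 1 − 0.05^(1/17) = 16.2% (one-sided 95% limit), but that measures imprecision and says nothing about misattribution. Third, one might picture a 4-week look-back at the last knee spanning all four knees. That needs back-to-back weeks and four home-worn knees, whereas section 3 schedules visits by convenience and device availability, and section 11 sends three knees home.

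**Conclusion.** The concern holds in a limited form. The order of the visit is plain from the text: falls are asked about only after Steps 5–8, so a home fall may go unasked for most or all of a 2–6 hour visit unless the participant mentions it. The absence of a stated recall period is equally plain. That falls could then be attributed to the wrong knee is an open possibility, conditional on the unseen form; the window shares are illustrations resting on assumed look-backs and a constant fall rate.

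Two neighbouring inconsistencies affect the remedy. Step 10 repeats only Steps 4–8, so read literally the fall survey is not repeated for each knee. Section 11 and Steps 4 and 10 disagree on whether the powered knee goes home, so a recall period tied to the home week is undefined for that knee. This is a modest, inexpensive improvement in safety information and data quality that should be made; it does not undermine the planned analyses.

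**What to change.** - Move the fall survey from Step 9 to the start of each return visit, before Step 5, so that the responsible investigator has the answer before testing begins. What follows from the answer is a clinical matter outside this point.
- Limit it to falls and near-falls since the current knee was fitted, recording the date and the knee worn.
- Record stumbles and harness catches during Steps 5–8 separately, so that lab and home events are not mixed.
- Leave the other questionnaires at Step 9.
- Make sure the fall survey lies within the steps that Step 10 repeats for each knee.
- Reconcile section 11 with Steps 4 and 10 on which knees go home, so that the recall period is defined for the powered knee.
- Optional: give the same survey once at Step 3 for the participant's own knee. The planned comparison is within participants among the study knees and does not depend on it.

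The cost is a small reordering of the visit, a wording change in the protocol and a few minutes of work. The survey itself is already planned.

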## **Protocol for Personalizing MPK Prescription for Individuals With Transfemoral Amputation**

### **1. Study Aim, Background and Design**

**Background:** Published data shows approximately 35% of service members who sustain an amputation have it occur at the transfemoral level. Significant evidence indicates microprocessor knees (MPKs) have numerous benefits over non-MPKs for individuals with transfemoral amputation (TFA) including improved gait, safety, comfort, confidence, reduced falls, balance, patient satisfaction and reduced energy expenditure, greater ease in negotiating varying terrains, improvements in multi-tasking and cost effectiveness, such that MPK technology should be considered current state-of-the-art in TFA prosthesis prescription. However, studies which currently exist on MPK technology tend to lump the various knees together as a group rather than teasing out differences between the individual MPK technology and what types of patients are best suited for each. Therefore, a gap exists in clinical knowledge forcing clinicians to choose componentry based on reimbursement or their past experiences with an MPK, rather than detailed evidence supporting the use of one MPK for a certain individual. In this proposal, we will assess the biomechanical function and patient reported outcomes of each subject while they are using three commercially available MPKs and a research grade powered knee, addressing the FY20 OPORP Focus Areas “Prosthetic Device Function” and “Prosthetic Device Form”.

**Hypothesis/Objective:** Our *objective* is to personalize the prosthetic prescription process by creating a clinical decision algorithm for selection of an ideal MPK for an individual patient with transfemoral amputation (TFA) based on objective and patient reported data collected from that specific user. We test the *central hypothesis* that biomechanical and patient perceived differences will be detectable and predictable between different MPK components within a certain individual allowing for the creation of the first ever clinical decision algorithm for MPK component selection.

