**Specific Aims:** Aim 1 will assess functional performance associated with use and wear of three different commercially available MPKs and one research grade powered knee in 17 individuals with TFA. Aim 2 will assess subjective patient reported preferences associated with use of the same four prosthetic knees along with collection of subject specific anthropomorphic characteristics that may correlate with MPK choice. Aim 3 will generate the clinical decision algorithm for MPK selection.

**Study Design:** Our study revolves around clinical tests and outcomes measures to evaluate the biomechanical performance and patient reported outcomes of three different commercially available MPKs and a single research grade powered knee in individuals with a TFA. We will test the hypothesis that differences will emerge between individuals when wearing the different knees and that these differences will be predictable. Subjects will ambulate over various terrains to simulate community ambulation with each MPK (Aim 1) allowing for assessment of the functional performance of each MPK. Through collection of individual anthropomorphic data and psychometric outcomes measures (Aim 2), we predict individual preferences and biomechanical improvements will emerge between the various MPKs

allowing for the generation of a clinical decision algorithm for MPKs (Aim 3).

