### **3. Study Procedures**

Upon recruitment and informed consent, participants will proceed through the following protocol steps until they have been fit with all 4 prosthetic devices in total.

*Randomization & Blinding:* The order with which each subject will be fit with an MPK will be randomized using a random number generator prior to enrollment. Subjects will not be blinded to device type as appearance of each device is a variable that may influence patient reported outcomes. Blinding of study personnel is not possible given that component-specific knowledge is required to tune each of the different MPKs. Data will be blinded for data analysis procedures to reduce any potential bias.

*Study procedures:*

1. Each device will be measured for length (overall build height) and weight prior to use in the study. Weight of devices will not be controlled due to anticipated effects on the outcomes and thus the final best selection.
2. Anthropomorphic data will be collected from each subject to include cause of amputation, K-level, waist circumference, leg length, residual limb length, build height between distal residual limb and knee center, weight, height, BMI, gender and age. These variables are unique characteristics associated with an individual which may have an impact on their successful use with one device over another. This data will only need to be collected once from each individual participant.
3. Subjects will be administered the Patient Scales of Preference and Importance survey to understand how they individually rank priorities with regards to their prosthetic care and aspects of their daily life. The AMPnoPro will be administered to the subject while they are not wearing their prosthesis to attempt simulation of a patient with a new amputation that has gone through physical therapy and ready for a definitive prosthesis. AMPnoPro has been shown to be predictive of the functional level of an amputee. [1]

Subjects will then undergo fitting and alignment of the prosthetic knees in a randomized order.

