### Statistical & data analysis plan

A repeated measures ANOVA with within factor MPK will be used to assess differences across treatment for Aims 1 and 2, provided assumptions are met. In the event of missing data or violation, a linear mixed models procedure, which does not assume compound symmetry, will be considered. Bonferroni-Holmes correction will be made to control for family-wise error rate. Samples size calculations are outlined below. Estimated effect size was calculated using Cohen's d for within factor designs [71], assuming a correlation among repeated measures of 0.5. Effect sizes were then converted to Cohen's f for sample size estimations using G\*Power. [72] **Aim 1: Comparison of clinical outcome measures on MPKs.** A Borg RPE of 2 (pooled SD= 2) was deemed clinically relevant for this study, resulting in an effect size of 1. Gait variability index effect size was based upon minimally detectable change (MDC) cited in [73]. An MDC of 8 and hypothesized pooled SD of 6, produced an effect size of 1.3. These data indicate a sample size of approximately 9 will achieve 90% power. The sample size proposed in this study (N=12) should ensure adequate power, even in the event of attrition or slightly higher variability. **Aim 2: Patient reported outcomes.** Resnik & Borgia (2011) have suggested a MDC of 10.3 (90% CI) for OPUS lower limb function.[61] Effect size for this study was calculated using MDC of 10 and a pooled SD of 7.7, assuming higher variability than previously reported SD's for upper

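### Step 10 repeats only Steps 4 to 8 for the later knees, leaving out Step 9, the only step that gives the per-knee questionnaires needed for Aim 2

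*Combined protocol and SAP*

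**What the plan says.** Section 3 sets out ten numbered steps and opens by saying that "participants will proceed through the following protocol steps until they have been fit with all 4 prosthetic devices in total". Steps 1 to 3 cover device measurements, participant characteristics and baseline assessments. Steps 4 to 8 cover fitting, the one-week acclimation and the laboratory tests for a knee. Step 9 then gives the questionnaires: "Subjects will then fill out the OPUS HRQOL, LEFS, PEQ, Veteran SF-36, and fall history survey". It says they are to capture perceived performance and "health related quality of life factors associated with use of each device".

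Step 10 governs the remaining knees: "Subjects will repeat Steps 4-8 with periods of rest provided as necessary until they have completed the full protocol for each" of the three commercial knees and the powered knee.

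Other sections bear on how often the questionnaires are needed:
- Section 1, Background: "we will assess the biomechanical function and patient reported outcomes of each subject while they are using three commercially available MPKs" and a powered knee.
- Section 1, Specific Aims: "Aim 2 will assess subjective patient reported preferences associated with use of the same four prosthetic knees".
- Statistical & data analysis plan: "A repeated measures ANOVA with within factor MPK will be used to assess differences across treatment for Aims 1 and 2". A linear mixed model is held in reserve for missing data or violated assumptions.
- Section 3, Step 2, on participant characteristics: "This data will only need to be collected once from each individual participant". Step 9 carries no such remark.

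**The concern.** Step 10 is the working instruction for three of the four knees. Its step range ends one step before the questionnaires, and no other passage schedules them for those knees. For the first knee, the wording of Step 9 places them after the treadmill test in Step 8. For knees two to four, no step places them.

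Aim 2 compares knees within a person, so it needs one questionnaire set per knee per person. Staff who follow the range would collect one set per person, for whichever knee came first in that person's random order. Staff who notice the conflict must still decide when to give the later sets. Section 3 allows sessions to extend over a few months, so a set completed at the end would rest on recall.

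The fall history survey is also in Step 9, and Section 4 names falls as the primary risk. On the literal reading, that survey too is lost for knees two to four. Self-report inside the range, such as the Borg RPE in Step 5, is not affected.

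**Working it through.** **1. The passages side by side**

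| Place | What it implies for the questionnaires |
|---|---|
| Step 10, step range | Not repeated after the first knee |
| Step 10, end of the sentence | Full protocol completed on every knee |
| Step 9 | Relates to the use of each device |
| Section 1, Background and Aim 2 | Patient-reported data on all four knees |
| Statistical plan | Knee is a within-person factor for Aim 2 |

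Only the step range points to a single collection. Step 3 also gives a survey, but it ranks the person's priorities before any study knee is fitted and cannot stand in for a per-knee measure.

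**2. The plan's own sample size assumes four scores per person**

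Inputs from the statistical plan: PEQ difference 1.1, SD 1.25, correlation between repeated measures 0.5, and N = 9 for 80% power. The plan gives neither alpha nor the conversion from d to f. I assume alpha 0.05, sphericity and f = d/2.

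- d = 1.1/1.25 = 0.88; f = 0.88/2 = 0.44.
- Noncentrality λ = f² × N × m/(1 − ρ), with df (m − 1) and (N − 1)(m − 1).
- With m = 4 and N = 9: λ = 0.1936 × 9 × 4/0.5 = 13.9, df 3 and 24, power 83.4%. The smallest N reaching 80% is 9, as the plan states.
- With m = 3 the smallest N is 10 (power at N = 9 is 75.2%). With m = 2 it is 13 (63.9%).

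On these assumptions, the stated N fits one score on each of four knees, which the literal Step 10 does not deliver.

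**3. Data available under each reading**

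| | Intended | Step range followed |
|---|---|---|
| N = 17 (Sections 1 and 2) | 17 × 4 = 68 sets | 17 sets |
| N = 12 (statistical plan) | 12 × 4 = 48 sets | 12 sets |

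The loss is 1 − 17/68 = 75% (equally 1 − 12/48).

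**4. Why the fallback does not help**

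With one record per person, each person is seen on one knee only. There is no within-person difference to estimate, and the person variance cannot be separated from the residual variance. A mixed model could then compare knees only between people.

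**5. Illustration of what such a between-person comparison could detect**

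The documents plan no such test. For four means whose largest difference is d, f runs from d × √(1/8) = 0.311 to d/2 = 0.44. Seventeen people over four knees is about 4 per knee, treated here as an even split.

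- Between-person: λ = f² × N, df 3 and 13. λ = 1.65 at f = 0.311 and 3.29 at f = 0.44.
- Within-person, four sets: λ = f² × 17 × 4/0.5, df 3 and 48. λ = 13.2 and 26.3.

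| PEQ power | Between-person, one set | Within-person, four sets |
|---|---|---|
| N = 17, alpha 0.05 | 13.3% to 23.0% | 84.5% to 99.2% |
| N = 17, alpha 0.01 | 3.6% to 7.4% | 63.7% to 95.7% |
| N = 17, alpha 0.10 | 22.6% to 35.5% | 91.2% to 99.7% |
| N = 12, alpha 0.05 | 9.8% to 15.2% | 66.9% to 94.1% |

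In each cell the low figure is for f = 0.311 and the high figure for f = 0.44.

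**The case against.** The strongest reply is that the intent is plain where the slip occurs. The same sentence requires the whole protocol on every knee, and the step just above speaks of each device. A careful team would give the questionnaires four times. The 75% loss needs staff to obey the digits and ignore the words around them. There is also a middle reading, in which four sets are collected and only their timing is unclear. The loss therefore runs from 0% to 75%, and the documents point strongly towards 0%.

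That stands as a limit on severity. It does not remove the contradiction: the digits are what a visit schedule would be built from, and no passage restates them correctly.

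Some supporting arguments are weaker than others. The opening sentence of Section 3 does not say that every step repeats for every device, and Steps 1 to 3 do not. The once-only remark in Step 2 proves little, since Step 3 has no such remark and is not repeated either. The case does not depend on these two.

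The power figures are illustration only. Their low end, f = 0.311, does not reproduce the plan's N = 9: it gives 51% power there and needs N = 16. The figures for f = 0.44 are the ones consistent with the plan. The inconsistency holds without any of them.

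Finally, correcting the range alone would carry Step 9's place in the sequence to every knee, so an extra clause on timing is not strictly needed. It is still worth one line, because it rules out later recall explicitly.

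**Conclusion.** The concern holds. Step 10 as written leaves the Aim 2 questionnaires out of the schedule for knees two to four, and it contradicts Step 9, the rest of its own sentence, Aim 2 and the planned analysis. It is probably a numbering slip, so it should be fixed but is not fatal to the design. On the intended reading nothing is lost. On the literal reading three quarters of the questionnaire sets are never collected and the planned within-person comparison for Aim 2 cannot be made.

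This conclusion rests on the text and on counting sets. Only the power figures depend on assumptions: alpha, the conversion from d to f, sphericity for the within-person test, and an even split for the between-person one.

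**What to change.** In Step 10, change the repeated range to Steps 4-9. Add one clause stating that the Step 9 questionnaires are completed at each knee's test visit, before the next knee is fitted, so that no knee is rated by later recall. Check that the visit schedule and data collection forms carry a questionnaire set for each of the four knees.

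The cost is one digit and one clause. Step 9 puts the questionnaires at 30 to 45 minutes, so four knees take 4 × 30 = 120 to 4 × 45 = 180 minutes, or 2 to 3 hours per person in total. The intended reading already includes that time, so nothing is added to it.
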